3.0 BACKGROUND AND SIGNIFICANCE

3.1 Background and Scientific Rationale

There are no proven treatments for coronavirus disease (COVID-19) and associated pneumonia caused by Severe Acute Respiratory Syndrome Coronavirus 2 (SARS-CoV-2). Recent experience in China suggests that convalescent immune plasma (CIP) may be an effective treatment for COVID-19. In the pandemic situation where there are no vaccines for COVID-19, specific antibodies in convalescent plasma induced by infection may provide passive protective immunity. Passive antibody therapy was the first immunotherapy dating back to the 1890s for the treatment of infectious diseases before the development of antibiotics 1940s^{1, 2}. Experience from prior outbreaks with other coronaviruses, such as SARS-CoV-1 shows that such convalescent plasma contains neutralizing antibodies to the relevant virus³. In SARS-CoV-2, passive antibody therapy from CIP probably provided protection by viral neutralization. CIP was also used in the 2013 Ebola epidemic. A small non-randomized study in Sierra Leone revealed a significant increase in survival for who received CIP⁴. CIP administration is the only approach that provides immediate immunity to patients who have been exposed or who have active disease.

This approach is immediately available from individuals who have recovered, are viral free, and can donate immune plasma (IP) containing high titer neutralizing antibodies. Passive antibody therapy can be given to a patient recently exposed or a patient who is developing an infection with COVID-19 by obtaining plasma units from immune individuals by standard plasmapheresis using FDA-approved blood banking procedures, cross matching the unit(s) to the recipients and infusing the unit(s) using standard

transfusion procedures for blood products. Based on the safety and long-term experience with plasma infusions, plasma exchanges, and other procedures involving plasma or plasma product, this protocol was designed as a phase II single arm trial that involves the administration of antibodies to a given agent to a susceptible individual for the purpose of preventing or treating an infectious disease due to that agent.

The only antibody formulation that is available for emergent use is that found in convalescent plasma. As more individuals contract COVID-19 and recover, the number of potential donors will increase.

The principle of passive antibody therapy is that it is more effective when used for prophylaxis than for treatment of disease. When used for therapy, antibody is most effective when administered shortly after the onset of symptoms. The reason for temporal variation in efficacy is not well understood but could reflect that passive antibody works by neutralizing the initial inoculum, which is likely to be much smaller than that of established disease. Alternatively, antibodies may dampen the early inflammatory response leaving the infected individual asymptomatic⁵. For example, antibody therapy for pneumococcal pneumonia was most effective when given shortly after the onset of symptoms and was of no benefit if antibody therapy was delayed beyond the third day of disease⁶. For passive antibody therapy to be effective, a sufficient amount of antibody must be infused. The antibody will circulate in the blood, reach tissues, and provide protection against infection. Depending on the type of antibody, amount, and composition, the half-life can vary from weeks to months. It is under these circumstances, *we plan to treat patients who are sick enough to be hospitalized before the onset of overwhelming disease involving a systemic inflammatory response, sepsis, and/or ARDS.*

3.2 Experience with the use of convalescent immune plasma against coronavirus diseases

In the 21st century, there were two coronavirus epidemics associated with high mortality. The SARS outbreak in 2003 and MERS outbreak in 2012 had high mortalities and absence of effective therapies which led to the use of convalescent immune plasma. The largest study with SARS using convalescent immune plasma involved the treatment of 80 patients in Hong Kong⁷. **Patients treated before day 14 after onset of symptoms had an improved prognosis as measured by discharge from hospital before day 22.** Furthermore, those who were RT-PCR positive and seronegative for coronavirus at the time of therapy had improved prognosis. Three seriously ill patients recovered from SARS in Taiwan were treated with 500 ml of convalescent plasma which led to a reduction in plasma virus titer⁸. Three patients with MERS in South Korea were treated with convalescent plasma, but only two of the recipients had neutralizing antibody in their plasma⁹. The results suggests that providing passive antibodies may suppress the development of high titers of neutralizing antibodies to the pathogen¹⁰. The analysis of 99 samples of convalescent sera from patients with MERS showed that 87 had neutralizing antibody with a geometric mean titer of 1:61. These data suggest that antibody declines with time and/or that few patients make high titer responses. There are reports that convalescent plasma was used for therapy of patients with COVID-19 in China during the current outbreak. Although few details are available from the Chinese experience and published studies involved small numbers of patients, the available information suggests that convalescent plasma administration reduces viral load and was safe. Because of these early suggestions of benefit, it is ethically complex to conduct a placebo-controlled trial, therefore we propose to use a comparator group of patients who have been treated at UVA Medical Center prior to the start of this trial.

4.0 ELIGIBILITY

4.1 Inclusion Criteria for Enrollment as a Plasma Recipient

- Patients must be 18 years of age or older
- Patients hospitalized with COVID-19 respiratory symptoms and confirmation via SARS-CoV-2 RT-PCR testing.

- Patient positive for COVID-19 with respiratory symptoms within 72 hours of admission (not in ICU or on high flow oxygen)
- Patient or surrogate is willing and able to provide written informed consent and comply with all protocol requirements.
- Patients with hematologic malignancies or solid tumors are eligible.
- Patients with autoimmune disorders are eligible.
- Patients with immunodeficiency or organ or stem cell transplant are eligible.
- Patients who have received or are receiving hydroxychloroquine or chloroquine are eligible (will be taken off the drug at enrollment)
- Prior use of IVIG is allowed but the investigator should consider the potential for a hyper-coagulable state

4.2 Exclusion Criteria for Plasma Recipients

- Patients requiring mechanical ventilation or >6 liters per minute nasal cannula oxygen
- Patients on other anti-COVID-19 treatment trials (for example, those being treated with tocilizumab (anti-IL-6 receptor), Siltuximab (anti-IL-2), or Remdesivir).
- A pre-existing condition or use of a medication that, in the opinion of the site investigator, may place the individual at a substantially increased risk due to study participation
- Contraindication to transfusion or history of prior reactions to transfusion blood products.
- Medical conditions for which receipt of 500-600 mL of intravenous fluid may be dangerous to the subject (e.g., decompensated congestive heart failure).

4.3 Control Group (obtained via chart review and includes control specimens)

Inclusion Criteria:

1. Admitted to a “floor” bed (non-ICU bed) at UVAMC on/after March 30, 2020 due to confirmed COVID-19 disease
2. Age \geq 18 years of age

Exclusion Criteria:

1. Requiring mechanical ventilation or >6 liters per minute nasal cannula upon admission
2. Participation in other interventional anti-COVID-19 treatment trials
3. Medical conditions for which receipt of 200-400mL of intravenous fluid may be dangerous to the subject (e.g. decompensated congestive heart failure)
4. Receipt of convalescent immune plasma for treatment of COVID-19

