¹ Measured by an anti-SARS-CoV-2 ELISA and serum antibody titer to SARS-CoV-2.

with confirmed COVID-19 disease through retrospective chart review.

In addition, the following Immunologic Controls will be used to meet secondary objectives described above:

1. PBMCs with 5-10 million cryopreserved cells per specimen will be obtained from the prospective COVID 19 Biorepository (2 timepoints per patient t (60 specimens total) and assessed for cellular and humoral immune responses.
2. Serum or plasma 500 UI each from up to 50 patients in the Covid-19 Biorepository will be collected (2 timepoints from each patient) (100 total specimens) will be evaluated for antibody and cytokine responses.

Study Population:

Inclusion Criteria for Enrollment

1. Patients must be 18 years of age or older
2. Patients hospitalized with COVID-19 respiratory symptoms within 72 hours of admission to a "floor" bed (non-ICU bed) and confirmation via SARS-CoV-2 RT-PCR testing.
3. Patient and/or surrogate is willing and able to provide written informed consent and comply with all protocol requirements.
4. Patients with hematologic malignancies or solid tumors are eligible.
5. Patients with autoimmune disorders are eligible.
6. Patients with immunodeficiency and organ or stem cell transplant recipients are eligible.
7. Patients who have received or are receiving hydroxychloroquine or chloroquine are eligible (but will be taken off the drug)
8. Prior use of IVIG is allowed but the investigator should consider the potential for a hyper-coagulable state.

Exclusion Criteria

1. Patients requiring mechanical ventilation or >6 liters per minute nasal cannula oxygen
2. Patients on other anti-COVID-19 trials being treated with tocilizumab (anti-IL-6 receptor), Siltuximab (anti-IL-2), Remdesivir, or other pharmacological trials that may be initiated hereafter.
3. A pre-existing condition or use of a medication that, in the opinion of the site investigator, may place the individual at a substantially increased risk due to study participation
4. Contraindication to transfusion or history of prior reactions to transfusion blood products.
5. Medical conditions for which receipt of 500-600 mL of intravenous fluid may be dangerous to the subject (e.g., decompensated congestive heart failure).

Clinical Controls (obtained via chart review):

1. Admitted to a "floor" bed (non-ICU bed) at UVAMC on/after March 30, 2020 due to confirmed COVID-19 disease using SARS-CoV-2 RT-PCR Testing

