2.3 Study Design

This is a single arm phase II trial to assess preliminary efficacy and confirm safety of infusions of anti-SARS-CoV-2 convalescent plasma in hospitalized patients with acute respiratory symptoms **with or without** confirmed interstitial COVID-19 pneumonia by CXR or chest CT. A total of 29 eligible subjects will be enrolled to receive high titer anti-SARS-CoV-2 plasma. Participants will be compared to a historical control group via retrospective chart review.

In addition, the following Immunologic Controls will be used to meet secondary objectives described above:

1. PBMCs with 5-10 million cryopreserved cells per specimen will be obtained from the prospective COVID 19 Biorepository (2 timepoints per patient t (60 specimens total) and assessed for cellular and humoral immune responses.
2. Serum or plasma 500 UI each from up to 50 patients in the Covid-19 Biorepository will be collected (2 timepoints from each patient) (100 total specimens) will be evaluated for antibody and cytokine responses.

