5.2.6 Subject Removal

Subjects should be removed from the trial if they require >6L/min supplemental oxygen or mechanical ventilation prior to receiving convalescent plasma infusion. Subjects may receive other medications that the investigator deems to be medically necessary.

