5.2.7 Enrollment, Screen Failures, and Study Completion

Patients are considered enrolled from time consented to participate until designated as a screen failure or have either been discontinued from the study or completed it. A screen failure is a patient who signed informed consent, but then was determined to be ineligible or withdraws from the study. Subjects are considered to have completed the study when they are followed through day 60 or have had an adverse event or death occurred prior to day 60.

Day -1 to 0 Baseline:

- A. Subject informed consent (obtained before performing study related activities)
- B. Baseline Evaluation at screening.
 1. Demographics (Age, sex ethnicity, race)
 2. Medical history (timing of exposure to COVID-19 source patient, acute and chronic medical condition, medications, allergies.) Any medical condition arising after consent should be recorded as AE.
 3. COVID-19 symptom screen (fevers, cough, shortness of breath, diarrhea, anosmia), onset of symptoms, source of contagion
 4. Vital signs

5. COVID-19 testing (RT-PCR) from nasopharyngeal, throat, tracheal aspirate or bronchoalveolar lavage and stool (optional) samples
6. Blood typing, CBC with differential, comprehensive metabolic panel
7. Serological testing: anti-SARS CoV-2 titers
8. Immune testing samples
9. Urine or serum pregnancy test for females of childbearing potential. Results from laboratory tests obtained up to 7 days before enrollment may be used for the pregnancy test.
10. Determination of eligibility as per inclusion/exclusion criteria, age, consent, positive for COVID-19, respiratory symptoms within 72 hours of admission

DAY 0 Baseline and Infusion:

1. Study Plasma Administration: 1-2 units of plasma will be transfused over 1-2 days. Time at start and end of infusion will be recorded and vital signs will be measured immediately prior to infusion, 10-20 minutes after start of infusion, at completion of infusion and 30-60 minutes after the end of the infusion
2. COVID-19 symptom screen (fevers, cough, shortness of breath)
3. Assessment of clinical status (8-point ordinal scale)
4. New medical conditions, concomitant medication, AE evaluation
5. Physical examination
6. COVID-19 testing (RT-PCR) from nasopharyngeal, throat or stool (optional) samples
7. Blood typing, CBC with differential, comprehensive metabolic panel, C-reactive protein
8. Serological testing: anti-SARS CoV-2 titers

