10.9 Subject Status Definitions

- Enrolled: All subjects who sign an informed consent will be considered enrolled on the study. All subjects consented on the study must be entered into Clinical Trials Office Database.
- Screen Failure: A subject who is withdrawn or discontinues from study screening prior to being on study is considered a screen failure. Screen failures are not considered a study accrual and will be replaced. Note: The IRB defines any individual that has signed an informed consent as an enrollment in this study and so screen failures should be reported to the IRB with enrollment numbers.
- On-Study: A subject is considered on-study on the date when the study team has confirmed the subject has met all of the inclusion and none of the exclusion criteria, and the treating physician/surgeon or study PI has signed off on the confirmation.
- On-Treatment: A subject is considered on-treatment on the date that they receive the first study treatment. A subject who is withdrawn or discontinues from the study after receiving at least 1 infusion is considered a discontinuation and will not be replaced.
- On Follow-up: A subject is considered on follow-up on the date that they have met any of the criteria in section 4.0.
- Off-Study: A subject is considered off-study if they are removed from the study for any of the reasons listed in section 4.0 or if they have completed all study assessments through follow-up.
- Immunologic Controls: A subject for whom biospecimen is obtained from the COVID-19 Biorepository.

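### The control definition has no end date and does not exclude people who consented to this trial, so a subject removed before infusion can be counted as a clinical control

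*Combined protocol and SAP*

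**What the plan says.** **Who the controls are.** Section 2.3 states: "Participants will be compared to a historical control group via retrospective chart review". Section 3.2 proposes "a comparator group of patients who have been treated at UVA Medical Center prior to the start of this trial". Section 7.1 calls the group historic and sets it at 29 patients, matched on gender and on age to within 5 years.

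**Who may be selected.** The operative criteria differ from that description. Section 4.3 takes floor-bed adults admitted "at UVAMC on/after March 30, 2020 due to confirmed COVID-19 disease", and section 1.0 takes those admitted "at UVAMC on/after March 30, 2020 due to confirmed COVID-19 disease using SARS-CoV-2 RT-PCR Testing". Both have a start date only. The exclusions in 4.3 are high oxygen need or ventilation at admission, participation in other interventional COVID-19 treatment trials, conditions that make a fluid load dangerous, and having received convalescent plasma. Section 1.0 lists only the last of these.

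**What happens to subjects who worsen before infusion.** Section 5.2.6: "Subjects should be removed from the trial if they require >6L/min supplemental oxygen or mechanical ventilation prior to receiving convalescent plasma infusion". Section 5.2.7: "A screen failure is a patient who signed informed consent, but then was determined to be ineligible or withdraws from the study". Section 10.9: "Screen failures are not considered a study accrual and will be replaced". Section 10.9 limits screen failure to the period before a subject is on-study. It does not say how an on-study subject removed before infusion is classified.

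**How ICU transfer is tested.** Sections 7.1 and 9.1 compare the ICU rate with a fixed 50% and reject if 8 or fewer of 29 evaluable patients go to the ICU. Section 9.1 names no between-group test against the clinical controls for ICU transfer or mortality.

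**The concern.** Whoever abstracts the charts will work from the criteria in 4.3, not from the rationale in 3.2. Under 4.3, admissions during the trial are open for selection, and nothing bars a person who consented to this trial and was never infused.

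Removal under 5.2.6 is triggered by respiratory decline, which is also a path to ICU transfer. A subject with a poor early course can therefore leave the plasma group and be counted among its controls. Both shifts favour plasma, and neither reflects an effect of plasma.

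The control comparison matters because sections 1.0 and 2.3 present it as the study's comparison of outcomes. For 28-day mortality the plan gives no fixed benchmark, so the controls are the only comparator it offers.

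**Working it through.** **Eligibility check.** Take a consented adult on a floor bed with PCR-confirmed disease who later needs more than 6 L/min oxygen and is removed uninfused. Against each exclusion in 4.3:
- Severity is judged at admission, so later worsening does not exclude.
- The trial exclusion covers other trials, so consent to this one does not exclude. Entering another trial after removal would.
- The plasma exclusion needs receipt, and there was none.
- Fluid risk may exclude. However, a subject who passed the recipient criterion in 4.2 (500-600 mL) would normally pass the control criterion (200-400 mL).
- Matching (7.1) uses gender and age, not calendar time or trial status.

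The patient can qualify.

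**The plan's own figure.** For a one-sample test of 50% against 25%, two-sided 0.05, 80% power:

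n = [(1.960 × √(0.5 × 0.5) + 0.842 × √(0.25 × 0.75)) / 0.25]² = 28.9, so 29. Power at 29 is 80.1%.

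The figure reproduces under the normal approximation. Counted exactly, the rule of 8 or fewer has a one-sided error of 1.2% at a true rate of 50%. No control data enter this rule. (Its exact power is 71.3%, which is a separate matter.)

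**Control side.** From the plan: 29 controls and a 50% ICU rate. Assumed: k removed subjects among the controls, with ICU risk q of 80% to 100%.

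Control rate = ((29 − k) × 0.50 + k × q) / 29, so each subject adds (q − 0.50)/29. That is 0.30/29 = 1.0 point at 80% and 0.50/29 = 1.7 points at 100%.

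The plan names no test, so I assumed an unpaired pooled z-test with t and c ICU admissions among 29 recipients and 29 controls: z = ((c − t)/29) / √(p(1 − p) × 2/29), p = (t + c)/58, rejecting in favour of plasma when z > 1.960. All outcomes were enumerated exactly, with a true recipient rate of 50% (no effect).

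| k | Control rate, q = 80% to 100% | Chance of a false finding for plasma |
|---|---|---|
| 0 | 50.0% | 2.4% |
| 1 | 51.0% to 51.7% | 2.9% to 3.1% |
| 3 | 53.1% to 55.2% | 4.0% to 5.3% |
| 6 | 56.2% to 60.3% | 6.3% to 10.6% |

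**Plasma side.** Suppose m subjects are removed and replaced until 29 are infused, with an overall rate of 50% and no effect. Recipient rate = (0.50 × (29 + m) − m × q)/29. For m = 3 this is (16 − 2.4)/29 = 46.9% at q = 80% and (16 − 3)/29 = 44.8% at q = 100%. Then:
- with clean controls, the z-test error is 4.1% to 5.6%;
- with the same three counted as controls, it is 6.5% to 11.2%;
- for the fixed-50% rule, the error rises from 1.2% to between 2.7% and 4.4%. This comes from removal and replacement, not from the controls.

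No mortality calculation is given, because the documents state no mortality rate.

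**The case against.** **The plan already says the controls are historical.** If 3.2 is read together with the start date in 4.3, the window closes at the start of the trial and no trial subject can be a control. That is a fair reading, and it makes the defect a contradiction rather than a certain bias. It does not cure 4.3, which is the list that will be applied.

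**A reader might infer that the control ICU rate is inflated.** The documents support only that it can be. Such subjects must exist, must be admitted under the open-ended reading, and must then be picked in the matching. Section 5.2.7 and Table I schedule screening on day -1 to 0 and infusion from day 0, so the planned interval for removal is about a day.

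**A reader might infer that the primary ICU test is compromised through the controls.** It is not: the rule uses a fixed 50%.

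**A reader might put the effect at 14-28% of the 25-point target.** That comes from two to four subjects at 100% ICU risk (2 × 0.5/29 = 3.4 points; 4 × 0.5/29 = 6.9 points). Neither the count nor the 100% is in the documents, and 5.2.6 also removes for oxygen need alone, which the plan does not equate with ICU transfer.

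**A reader might infer that anyone judged too high-risk for the trial becomes a control.** Section 4.3 excludes those at risk from fluid load. Only other reasons, such as a transfusion contraindication, leave that route open.

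**Closing the window does not repair the plasma side.** This stands. Removed subjects still leave the plasma group, while controls who worsen soon after admission still count.

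**Conclusion.** The concern holds in a limited form. Sections 1.0 and 4.3 conflict with 2.3, 3.2 and 7.1 on when controls were treated, and no criterion stops this trial's own removed, uninfused subjects from serving as controls. Following 4.3 as written can bias the control comparison of both primary endpoints towards plasma.

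The text and the direction are firm, since removal depends on respiratory worsening. The size is not, because the documents give no trial start date, removal count, control-pool size or ICU risk after removal. The range of 1.0-1.7 points per subject rests on an assumed ICU risk of 80-100%. The rise from 2.4% to about 4.0-5.3% rests also on three such subjects and an assumed unpaired z-test.

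**What to change.** 1. In 1.0 and 4.3, state that no one who consented to this trial may be a clinical control. This is one sentence, and it removes the crossover whichever control window is chosen.
2. Reconcile the window with 3.2. Either give an end date before the first recipient's consent or, if later admissions are needed, say so in 2.3, 3.2 and 7.1 and report results by calendar period. Choosing between prior and concurrent controls is a legitimate trade-off, but the plan should make the choice openly.
3. Report ICU transfer and 28-day mortality also for all consented, eligible subjects, infused or not. Define evaluable in 7.1 and 9.1, and state in 10.9 how an on-study subject removed before infusion is classified. This addresses the plasma-side shift that items 1 and 2 leave in place.

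Cost: wording, follow-up of removed subjects for the two endpoints, and a smaller control pool. The loss of pool cannot be sized from the documents. With an end date, admissions between March 30, 2020 and first consent might yield fewer than 29 matched controls, which is why item 2 keeps the second option.

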7.0 STATISTICAL CONSIDERATIONS

7.1 Statistical Analyses

Twenty-nine evaluable patients will have 80% power to declare a significant decrease in ICU admissions from a historical control of 50% of hospitalized patients to 25% with a two-sided type I error of 0.05 (reject ICU admission rate=50% if only 8 or less patients are admitted to ICU among 29 evaluable patients). The historic control group will consist of 29 patients who are gender and age (within 5 years) matched.

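### Chart-review controls need neither respiratory symptoms nor freedom from transfusion contraindications, so the control ICU rate comes from a wider population than the recipients

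*Combined protocol and SAP*

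**What the plan says.** **Recipients.** Section 4.1 admits "Patients hospitalized with COVID-19 respiratory symptoms and confirmation via SARS-CoV-2 RT-PCR testing". A second criterion repeats the symptom requirement and adds timing and location: "Patient positive for COVID-19 with respiratory symptoms within 72 hours of admission (not in ICU or on high flow oxygen". Section 4.2 excludes "Contraindication to transfusion or history of prior reactions to transfusion blood products".

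**Controls.** Section 4.3 asks for a floor admission at the centre "on/after March 30, 2020 due to confirmed COVID-19 disease" and age 18 or over. It has four exclusions:
- "Requiring mechanical ventilation or >6 liters per minute nasal cannula upon admission"
- participation in another interventional COVID-19 trial
- "Medical conditions for which receipt of 200-400mL of intravenous fluid may be dangerous to the subject"
- receipt of convalescent plasma

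The control list in the Summary names RT-PCR confirmation, but it has no symptom or transfusion criterion either.

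**Matching and use.** Section 7.1 states: "The historic control group will consist of 29 patients who are gender and age (within 5 years) matched". The Summary and sections 2.3 and 3.2 make this group the comparator. ICU transfer is a primary endpoint (7.3.1).

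**The concern.** Without randomisation, eligibility is one of the few means this design has of making the two groups alike. Section 4.3 goes part of the way. A fluid-tolerance exclusion for patients who will receive nothing makes sense only as an attempt at comparability. Yet the criterion closest to the endpoint, respiratory symptoms, is left out, and no reason is given.

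If some controls were admitted for COVID-19 without respiratory illness, their ICU risk is probably lower than that of patients who could have been recipients. The control ICU rate would then be too low as a benchmark, and a real benefit of plasma could be understated.

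**Working it through.** **1. The plan's own figure.** Inputs from 7.1 and 9.1 are p0 = 0.50, p1 = 0.25, two-sided alpha 0.05 and power 80%. By the one-sample normal approximation:

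n = [(1.960 × √(0.50 × 0.50) + 0.842 × √(0.25 × 0.75)) / (0.50 − 0.25)]² = 28.92, so 29, with power 80.1% at 29.

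The stated N reproduces. No chart-review control enters this formula or the rule of 8 or fewer of 29, so changing 4.3 alters neither. (Computed exactly, the rule has lower-tail error 0.0121 and power 71.3%. That is a separate matter.)

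**2. Criteria side by side.**

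| Criterion | Recipients (4.1, 4.2) | Controls (4.3) |
|---|---|---|
| Respiratory symptoms | required | not mentioned |
| Transfusion contraindication or prior reaction | excluded | not mentioned |
| Ventilation or >6 L/min | excluded | excluded, on admission |
| Other COVID-19 trials | excluded | excluded |
| Fluid intolerance | 500-600 mL | 200-400 mL |
| Investigator's opinion of risk | excluded | not mentioned |

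**3. Is the gap closed elsewhere?** Section 4.1 lists respiratory symptoms in addition to a positive test. The baseline symptom screen in 5.2.7 includes fever, diarrhea and anosmia beside cough and shortness of breath. The protocol thus does not treat COVID-19 illness as respiratory by definition. Matching uses age and gender only. The covariate adjustment in 9.1 is described with the immune-biomarker regressions, not with the ICU comparison.

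**4. Illustrative size.** The documents give neither the share f of controls without respiratory symptoms nor their ICU risk r. Assume f = 10-30%, r = 5-30%, and 50% in the remaining controls. The fall in the control ICU rate is f × (0.50 − r):
- smallest: 0.10 × (0.50 − 0.30) = 2.0 points
- largest: 0.30 × (0.50 − 0.05) = 13.5 points

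Among 29 controls this is 29 × 0.020 = 0.6 to 29 × 0.135 = 3.9 fewer expected ICU transfers.

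**5. The fixed-50% test, conditionally.** Suppose the 50% had been observed in a pool mixed in this way. The rate in symptomatic patients would be (0.50 − f × r) / (1 − f):
- f = 0.10, r = 0.30: 0.47 / 0.90 = 52.2%
- f = 0.30, r = 0.05: 0.485 / 0.70 = 69.3%

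If plasma halved those rates, to 26.1% and 34.6%, the exact binomial chance of 8 or fewer of 29 would be 66.3% and 27.8%, against 71.3% at 25%. The plan does not say where the 50% came from, so whether this applies is unknown.

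**The case against.** **The control criterion is narrower than it first looks.** Controls must be admitted because of COVID-19. A reader might infer that incidental positives enter the control group, but the wording excludes them. What remains is patients admitted for COVID-19 whose illness is not respiratory, and nothing in the documents shows how common they are. This stands, and it limits the likely size.

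**Transfusion risk is partly covered.** The fluid criterion mirrors volume-related risk, with the same heart-failure example. The gap is therefore mainly contraindications and prior reactions. A reader might infer that omitting these biases in favour of plasma and offsets the symptom effect. The documents link neither to ICU transfer, so no direction can be claimed.

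**Not every recipient criterion can be carried over.** The remaining exclusion rests on the investigator's opinion that a condition or medication "may place the individual at a substantially increased risk due to study participation". Chart-review controls do not participate, and an opinion of this kind cannot be read from a chart. That difference is inherent.

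**The formal rule does not use these controls.** A reader might infer that the mismatch undermines the sample size, or might express the 2 to 13.5 points as a share of the 25-point effect. Neither follows. The 25 points belong to a test against a fixed 50%, stated for hospitalized patients with no symptom restriction, and no formal test of ICU transfer against the 29 charts is specified.

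**Aligning these criteria will not by itself make the groups comparable.** Recipients may enter up to 72 hours after admission and are removed if they worsen before infusion (5.2.6), whereas controls are screened on admission. This is true, but it is a separate difference and no reason to keep an avoidable one.

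**Conclusion.** The point holds as an avoidable eligibility mismatch in a non-randomised comparison of a primary endpoint. That the criteria differ is certain from the text. That the symptom gap works against plasma is probable: it rests on the assumption that patients admitted without respiratory symptoms need the ICU less often. The effect of the transfusion gap is unclear, so no net direction is established for the two together.

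The 2 to 13.5 points depend entirely on assumed inputs and span almost sevenfold. They show that the effect could be anything from negligible to appreciable, not that it is large. The N = 29 calculation and the 8-of-29 rule stand as printed. The test against 50% is touched only if that figure came from patients like these controls.

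**What to change.** In 4.3, and in the matching list in the Summary, before matching is done:
- require COVID-19 respiratory symptoms at admission;
- exclude patients with a chart-documented contraindication to transfusion or a prior transfusion reaction;
- reconcile the fluid volumes, which read 500-600 mL in 4.2 and 200-400 mL in 4.3;
- leave out the investigator-opinion criterion, and say that it has no chart equivalent.

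The cost is protocol wording, a few extra chart-review fields and a somewhat smaller pool from which to match 29 controls. The Summary already lists symptom onset date, respiratory rate, oxygen saturation, oxygen requirement and comorbidities as baseline data, and provides for all relevant control data to come from charts. The added work is mainly recording symptom type and transfusion history. Neither the sample size nor the decision rule changes.
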